# 4.2 Secondary Endpoints

# 4.2.1 Overall Survival in All Randomized Subjects

Overall survival in All Randomized subjects is defined the same way as for the primary endpoint (for subjects with PD-L1 expressing tumors).

# 4.2.2 Progression-Free Survival per BICR in All Randomized Subjects

Progression-free survival in All Randomized subjects is defined the same way as for the primary endpoint (for subjects with PD-L1 expressing tumors).

## 4.2.3 Objective Response Rate per BICR in All Randomized Subjects

Objective response rate as assessed by BICR in subjects with PD-L1 expressing tumors and in All Randomized subjects are secondary endpoints for this study.

It is defined as the number of subjects with a best overall response (BOR) of CR or PR divided by the number of randomized subjects in the population for each treatment group. BOR is defined as the best response designation as determined by BICR per RECIST 1.1, recorded between the date of randomization and the date of objectively documented progression or the date of subsequent anti-cancer therapy (including tumor-directed radiotherapy and tumor-directed surgery), whichever occurs first. For subjects without documented progression or subsequent anti-cancer therapy, all available response designations will contribute to the BOR determination. For subjects who continue treatment beyond progression, the BOR will be determined based on response designations recorded up to the time of the initial RECIST 1.1-defined progression.

## 4.3 Exploratory Endpoints

# 4.3.1 Efficacy Exploratory Endpoints

# Progression-Free Survival per Investigator

Progression-free Survival as assessed by investigator in subjects with PD-L1 expressing tumors and in All Randomized subjects is defined similarly as the corresponding (primary) endpoints as assessed by BICR - except that only tumor assessments by investigator will be taken into account.

#### Objective Response Rate per Investigator

Objective response rate as assessed by investigator in subjects with PD-L1 expressing tumors and in All Randomized subjects is defined similarly as the corresponding (primary) endpoints as assessed by BICR - except that only tumor assessments by investigator will be taken into account.

## **Duration of Response**

Duration of Response (as assessed by BICR and as assessed by investigator) is defined as the time between the date of first documented response (CR or PR) to the date of the first disease progression, per RECIST 1.1 or death due to any cause, whichever occurs first. For subjects who neither progress nor die, the duration of objective response will be censored at the same time they were censored for the primary definition of PFS. DOR will be evaluated only for subjects whose BOR is CR or PR.

Survival rate, PFS rate and duration of Stable Disease (SD) are not positioned as objectives per protocol, but will be evaluated.

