# 4.1.2 Progression-Free Survival per BICR in All PD-L1 Expressing Subjects

For the purposes of the primary endpoints, PFS is as assessed by BICR in subjects with PD-L1 expressing tumors.

PFS is defined as the time from randomization to the date of the first documented PD per BICR or death due to any cause. Subjects without any baseline scan will be censored at the randomization date (regardless of death). Subjects who did not have any on-study tumor assessments and did not die (or died after initiation of the subsequent anti-cancer therapy) will be censored at the randomization date. Subjects who die without a reported prior PD per BICR (and die without start of subsequent therapy) will be considered to have progressed on the date of death. Subjects who did not have documented PD per BICR per RECIST1.1 criteria and who did not die, will be censored at the date of the last evaluable tumor assessment on or prior to initiation of the subsequent anti-cancer therapy. Subjects who started any subsequent anti-cancer therapy without a prior reported PD per BICR will be censored at the last tumor assessment on or prior to initiation of the subsequent anti-cancer therapy.

See Figure 4.1.2-1 for the graphical representation of this definition.

Figure 4.1.2-1: Graphical Representation of the Primary PFS Definition

rand = randomization, subs = subsequent therapy

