# **Duration of Stable Disease**

Duration of SD is defined as the time between the randomization date and the date of the first documented tumor progression (per RECIST 1.1) or death due to any cause, whichever occurs first. Censoring rules will be the same as for DOR analysis. It will be evaluated only for subjects whose BOR is SD.

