## 7.5.4.3 Endpoints Related to Best Overall Response

Duration of Response and Duration of SD (as assessed by BICR and by investigator) in each treatment group will be estimated using KM product-limit method for subjects who achieve PR or CR. Median values along with two-sided 95% CI will be calculated.

For DOR, type of event (PD, death) and status of subjects censored (received subsequent therapy, ongoing follow-up [current, non-current], off study [withdrew consent] will be presented by treatment arm.

Time to objective response (TTR as assessed by BICR and by investigator): summary statistics will be provided for each treatment group for subjects who achieve PR or CR. Cumulative Response Rates will be tabulated for Week 6, Week 12, Month 4, 6, 8, and 12, and overall Response Rate will be provided for each treatment group.

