- Assuming 158 PD-L1 expressing subjects randomized to the chemotherapy arm and considering the number of 102 PFS events observed so far, there would be an additional 158-102=56 subjects for whom a PFS event may still be expected per primary definition. However, per secondary definition which accounts for disease progression after subsequent therapy, a total of 135 PFS events per BICR were observed. Therefore, it is evident that for 135-102=33 subjects, PFS events per primary definition should not be expected.
- Event tracking in all randomized subjects across the three treatment arms indicated there are a total of 94 subjects are censored per primary definition due to withdrawal of consent, lost to follow-up, no scans or without PD/death after subsequent therapies. Assuming equal subject distribution across treatment arms and PD-L1 expression subgroups, it is estimated that 15 of these subjects would represent PD-L1 expressing subjects in the chemotherapy arm, thus reducing the potential pool of subjects for whom a PFS event could be expected even further.
- Therefore, among the 56 subjects without observed PFS events (per primary definition), only 56-33-15=8 subjects may contribute a PFS event per primary definition, whereas an additional 34 PFS events are needed to trigger the IA.

Based on the reasons stated above, the IA will be performed when 136 PFS events are observed or when a 12-month minimum follow-up (defined as the time from the date the last patient was randomized to the clinical cutoff date) is reached if the target number of events is unlikely to be reached among the PD-L1 expressing subjects in the chemotherapy arm. The table below provides the power based on different numbers of PFS events among PD-L1+ subjects in chemo arm using the same protocol assumption.

	Total number of PFS events for one	
PFS events among PD-	comparison (i.e. for N+I vs CT; and	
L1+ in chemo	for N+C vs CT)	Power
136	250	90%
121	218	85%
110	195	80%
100	175	75%

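### Duration of response is censored according to later outcome: responders who switch therapy without progression are censored at the pre-therapy scan if they stay event-free, but count as events if they later progress or die

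*SAP*

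**What the plan says.** **DOR.** SAP 4.3.1 measures DOR from first documented response "to the date of the first disease progression, per RECIST 1.1 or death due to any cause, whichever occurs first". Subsequent therapy does not cut this off. The only censoring rule is: "For subjects who neither progress nor die, the duration of objective response will be censored at the same time they were censored" for primary PFS. Protocol 8.3.3 has the same rule. A further SAP sentence limits DOR to subjects with a BOR of CR or PR.

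**Primary PFS (SAP 4.1.2).** "Subjects who started any subsequent anti-cancer therapy without a prior reported PD per BICR will be censored at the last tumor assessment" on or before that therapy. Deaths are handled to match: "Subjects who die without a reported prior PD per BICR (and die without start of subsequent therapy) will be considered to have progressed". A death after new therapy is therefore not a PFS event.

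**BOR (SAP 4.2.3).** Responses count up to documented progression or "the date of subsequent anti-cancer therapy (including tumor-directed radiotherapy and tumor-directed surgery), whichever occurs first".

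**Duration of stable disease (SD).** SAP 4.3.1 gives it the DOR censoring rules and adds: "It will be evaluated only for subjects whose BOR is SD". SAP 7.5.4.3 then says in one sentence that DOR and duration of SD "will be estimated using KM product-limit method for subjects who achieve PR or CR".

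**The concern.** Take two responders who start the same second-line treatment on the same day without progression. As written, the one who is alive and progression-free at the data cut is censored back at the last scan before the new therapy. The one who dies stays at risk throughout and ends with an event. Whether a subject is censored, and when, is therefore decided by the outcome under study. Kaplan-Meier estimation assumes that it is not.

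DOR would also not be comparable with the PFS and response results in the same report, because both of those stop at subsequent therapy. The result will be used: SAP Section 8 overlays the DOR curves of all three arms and reports medians, as part of judging the contribution of ipilimumab. Later immunotherapy is expected, since Protocol 8.1 monitors its use in the chemotherapy arm. SAP 2.5 requires scans to continue after subsequent therapy where feasible, so late progressions will be in the database.

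Duration of SD inherits the censoring problem. If it were computed in responders, it would not describe stable disease at all.

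**Working it through.** **1. Which rule covers a responder who starts subsequent therapy without progression?**

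| Later course | Primary PFS (SAP 4.1.2) | PFS without truncation (sensitivity analysis, SAP 7.5.2.2) | DOR as written (SAP 4.3.1) |
|---|---|---|---|
| Alive, no progression | Censored at last assessment on or before therapy | Censored using assessments after therapy | Censored at last assessment on or before therapy |
| Later progression or death | Censored at last assessment on or before therapy | Event | Event |

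DOR takes its events from the untruncated definition and its censoring dates from the truncated one. No other section supplies a different rule.

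**2. One responder.** The times are assumed; the documents give none. Response is at month 3 and the last scan on or before new therapy at month 6, with no progression. Primary PFS is censored at month 6 in every row. DOR with PFS-type censoring is 6 − 3 = 3 months, censored. DOR as written, with an event, is death month − 3.

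| Later course | DOR with PFS-type censoring | DOR as written |
|---|---|---|
| Alive, no progression | 3, censored | 3, censored |
| Death at month 9 | 3, censored | 9 − 3 = 6, event |
| Death at month 15 | 3, censored | 15 − 3 = 12, event |
| Death at month 24 | 3, censored | 24 − 3 = 21, event |

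The DOR end date passes the PFS censoring date in every death row. DOR as a length exceeds PFS as a length only when the interval after the PFS censoring date is longer than the time to response. At month 9 they are equal (6 and 6).

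**3. How common are events after subsequent therapy?** Appendix 7 reports 102 primary-definition BICR PFS events among PD-L1-expressing chemotherapy subjects. Without truncation, "a total of 135 PFS events per BICR were observed". The appendix's arithmetic reproduces: 135 − 102 = 33; 158 − 102 = 56; 56 − 33 − 15 = 8.

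- 33 / 135 = 24.4% of the untruncated events
- 33 / 158 = 20.9% of the estimated PD-L1-expressing chemotherapy subjects

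These are all subjects, not responders.

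**4. Direction of the effect.**

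*Against a fully untruncated curve.* The rule as written has the same events at the same times. Its risk sets are smaller, because switchers still event-free have been removed at their pre-therapy scan. Its curve therefore lies on or below the untruncated one.

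*Against PFS-type censoring.* The direction depends on the hazard after switching. An assumed exponential model was simulated with a median of 7 months before any switch. The proportion switching first and the median time from switch to event were varied. Kaplan-Meier medians in months:

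| Switch first | Censored at switch | Events counted, post-switch median 3 | 6 | 12 |
|---|---|---|---|---|
| 10% | 6.96 | 6.71 | 6.92 | 7.08 |
| 24.4% | 7.03 | 6.39 | 6.91 | 7.41 |
| 40% | 6.99 | 5.86 | 6.77 | 7.75 |

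Counting post-therapy events moves the median from about 7.0 to between 5.9 and 7.8. The model follows every switcher to an event, so it leaves out the further downward pull from censoring event-free switchers early.

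**5. Duration of SD.** SAP 4.3.1 restricts it to subjects with BOR of SD, while SAP 7.5.4.3 estimates it in subjects with PR or CR. Best overall response takes a single value per subject, so the two populations do not overlap and both instructions cannot be followed.

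**The case against.** **The sentence is incomplete rather than wrong.** DOR refers to the primary PFS definition, which is truncated at subsequent therapy, and SAP 7.5.4.3 lists receipt of subsequent therapy among the DOR censoring statuses. PFS-type censoring may well be what the sponsor meant, so how DOR will be programmed is not established. But the censoring clause expressly excludes subjects who progress or die. A reader might take the 7.5.4.3 status as proof of intent. It is not, because responders alive without progression after new therapy fall into that status under the literal rule too.

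**Counting events after subsequent therapy is a recognised choice.** SAP 7.5.2.2 notes that EMA treats the untruncated PFS definition as primary. That would defend a consistently untruncated DOR, which also uses assessments after therapy for subjects without an event. The rule as written does not do this.

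**DOR is exploratory and descriptive.** This stands. No alpha is attached, and no primary or secondary test, power figure or type I error is touched.

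**The duration-of-SD conflict is a drafting slip in a combined sentence.** Probably so, and SAP 4.3.1 is clear on the population. The analysis section still says otherwise and should be corrected.

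**Conclusion.** The concern holds as a defect in a stated rule. Among responders who switch therapy without progression, DOR censoring depends on the later outcome, and the result is inconsistent with primary PFS and BOR. The defect follows from the text and needs no numerical assumption. Appendix 7 shows that the situation is frequent in the PD-L1-expressing chemotherapy arm: 33 of about 158 subjects, where 158 is the SAP's own estimate.

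Three stronger readings are not supported:

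- **That median DOR is inflated.** Relative to PFS-type censoring the direction is open. The assumed model gives 5.9 to 7.8 months against about 7.0.
- **That the distortion favours an arm.** The documents give no switching rates by arm, and the sponsor was blinded to PFS events in the experimental arms.
- **That the number of affected responders is known.** Applying 20.9% to the 15%–45% response range in Protocol 1.1.1.2 would give about 5 to 15 control responders (158 × 0.15 ≈ 24 and 158 × 0.45 ≈ 71, each × 0.209). That assumes responders switch like everyone else. The 33 are also BICR events and say nothing about investigator-assessed DOR.

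The point should be corrected before DOR is reported, but it does not bear on the trial's confirmatory conclusions.

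**What to change.** In SAP 4.3.1 and Protocol 8.3.3, replace only the sentence containing "For subjects who neither progress nor die, the duration of objective response will be censored at the same time they were censored" with:

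> DOR uses the same event and censoring rules as the primary PFS definition (BICR or investigator, as applicable); responders who start subsequent anti-cancer therapy without prior PD are censored at the last tumor assessment on or before that therapy, regardless of later PD or death.

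Keep the SAP sentence that limits DOR to BOR of CR or PR. Duration of SD then inherits the corrected censoring through its existing cross-reference.

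If the sponsor also wants a DOR that runs through subsequent therapy, add it as a sensitivity analysis that counts both events and assessments after therapy.

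In SAP 7.5.4.3, split the combined sentence: DOR in subjects with BOR of CR or PR, duration of SD in subjects with BOR of SD, as 4.3.1 states.

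Cost: SAP and protocol wording, minor programming, and more censoring in DOR. No new data are needed.

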## **Survival Rate**

Overall survival rate at different timepoints, e.g. at 18, 24, and 36 months is defined as the probability that a subject is alive at 18, 24, and 36 months, respectively, following randomization. Overall survival rates at other timepoints are defined similarly.

### **PFS Rate**

PFS rate at different timepoints, e.g. at 6, 12, 18 and 24 months is defined as the probability that a subject has not progressed and is alive at 6, 12, 18 and 24 months, respectively, following randomization. PFS rates at other timepoints are defined similarly.

# **Duration of Stable Disease**

Duration of SD is defined as the time between the randomization date and the date of the first documented tumor progression (per RECIST 1.1) or death due to any cause, whichever occurs first. Censoring rules will be the same as for DOR analysis. It will be evaluated only for subjects whose BOR is SD.

#### PFS2/TSST

PFS on next-line therapy (PFS2) / Time To Second Subsequent Therapy (TSST) is defined as the time from randomization to the documented progression (radiographic or clinical progression) per investigator assessment after the next line of systemic therapy or start of the second next line systemic therapy or death from any cause, whichever occurs first. Subjects who were alive and without the second progression and without the second next line systemic therapy will be censored at last known alive date.

The following censoring rules will be applied for PFS2/TSST:

- Subjects who did not receive any subsequent anti-cancer systemic therapy:
  - Subjects who died, the death date is the event date;
  - Else the subject's PFS2/TSST is censored at the last known alive date.
- Subjects who received at least one subsequent anti-cancer systemic therapy:
  - Subjects who had a disease progression after the start of the first subsequent anti-cancer systemic therapy, this disease progression date is the event date;
  - Else if a subject died or start of the second next line systemic therapy, the date of min (death, start date of the second next line systemic therapy) is the event date;
  - Else the subject's PFS2/TSST is censored at the last known alive date.

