### **3.1.3 Follow-up Phase**

- Begins when the decision to discontinue a subject from study therapy is made (no further treatment with study therapy).
  - FU1 = 30 days from last dose ( $\pm 7$  days) or coinciding with the date of discontinuation ( $\pm 7$  days) if date of discontinuation is greater than 35 days after last dose
  - FU2 = 84 days from FU1 ( $\pm 7$  days).
- Subjects who discontinue treatment for reasons other than tumor progression will continue to have tumor assessments as per the schedule for the assigned treatment arm until confirmed disease progression, withdrawal of consent or lost to follow-up.
- Subjects will be followed for all AEs until these resolve, return to baseline or are deemed irreversible. All AEs will be documented for a minimum of 100 days after the last dose of study treatment.
- After completion of the first two follow-up visits, subjects will be followed every 3 months ( $\pm 14$  days) for survival via in-person visit or phone. Ad hoc survival data requests may be made during the study as well, particularly during database locks. Additional subsequent cancer therapy details such as regimen, setting of the regimen, line of therapy, start date and end date of each regimen, best response to the regimen and date of progression after second line therapy will be collected.
- The PRO questionnaires collection and biomarker sampling will continue as per time and event schedule. Study follow-up assessment data are to be collected as outlined in [Table 5.1-5](#).

The start of the trial is defined as first visit for first subject screened . End of trial is defined as the last visit or scheduled procedure shown in the Time & Events schedule for the last subject. Study

completion is defined as the final date on which data for the primary endpoint was or is expected to be collected, if this is not the same.

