### **8.3.3 Exploratory Endpoint(s)**

- Progression-free Survival (PFS) (as assessed by investigator) in subjects with PD-L1 expressing tumors and All Randomized subjects. PFS is defined the same way as for the primary and secondary endpoints (as assessed by BICR) - except that only PD assessments by investigator will be taken into account.
- Objective Response Rate (ORR) (as assessed by investigator) in subjects with PD-L1 expressing tumors and All Randomized subjects. ORR is defined the same way as for the primary and secondary endpoints (as assessed by BICR) - except that only tumor assessments by investigator will be taken into account.
- Duration of Response (DOR) (as assessed by BICR and as assessed by investigator) is defined as the time between the date of first documented response (CR or PR) to the date of the first disease progression, per RECIST 1.1 or death due to any cause, whichever occurs first. For subjects who neither progress nor die, the duration of objective response will be censored at the same time they were censored for the primary definition of PFS.
- PFS2/TSST in subjects with PD-L1 expressing tumors and all randomized subjects. PFS2/TSST is defined as the time from randomization to the date of investigator-defined documented second objective disease progression or start of second subsequent therapy or death due to any cause, whichever comes first. Clinical deterioration will not be considered as progression. Details for censoring will be provided in the SAP.
- Safety and tolerability objective will be measured by the incidence of adverse events (AEs), serious adverse events (SAEs), deaths, and laboratory abnormalities.
- PK will be measured using serum concentration-time data.

Assessments for other exploratory endpoints are discussed in other sections of the protocol, including biomarker analysis (Section 5.6), immunogenicity (Section 5.5), and outcomes research (Section 5.7). Corresponding endpoints will be detailed in the statistical analysis plan(s) (SAP[s]).

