# 3.3 Exploratory

- To assess PFS of nivolumab plus ipilimumab and nivolumab combined with fluorouracil plus cisplatin vs fluorouracil and cisplatin combination as assessed by investigators in subjects with PD-L1 expression ≥ 1% and in all randomized subjects.
- To assess ORR of nivolumab plus ipilimumab and nivolumab combined with fluorouracil plus cisplatin vs fluorouracil and cisplatin combination as assessed by investigators in subjects with PD-L1 expression ≥ 1% and in all randomized subjects.
- To assess Duration of Response (DOR) of nivolumab plus ipilimumab or nivolumab combined with fluorouracil plus cisplatin vs fluorouracil and cisplatin combination as assessed by BICR and by investigators in subjects with PD-L1 expression ≥ 1% and in all randomized subjects.
- To assess time from randomization to the date of investigator-defined documented second objective disease progression or start of second subsequent therapy or death due to any cause, whichever comes first (PFS2/TSST) of nivolumab plus ipilimumab (Arm A) or nivolumab combined with fluorouracil plus cisplatin (Arm B) vs fluorouracil and cisplatin combination (Arm C) as assessed by investigators in subjects with PD-L1 expression ≥ 1% and in all randomized subjects.
- To assess the overall safety and tolerability of treatment with nivolumab plus ipilimumab or nivolumab combined with fluorouracil plus cisplatin vs. fluorouracil and cisplatin combination.
- To characterize the PK of nivolumab plus ipilimumab or nivolumab combined with fluorouracil plus cisplatin.
- To characterize the immunogenicity of nivolumab plus ipilimumab or nivolumab combined with fluorouracil plus cisplatin.
- To characterize immune correlates of nivolumab plus ipilimumab, nivolumab combined with fluorouracil plus cisplatin, and fluorouracil and cisplatin combination.
- To evaluate the pharmacodynamic activity of nivolumab plus ipilimumab or nivolumab combined with fluorouracil plus cisplatin in the peripheral blood.

- To explore potential biomarkers associated with clinical efficacy (OS, PFS, and ORR) and/or with incidence of adverse events of nivolumab plus ipilimumab or nivolumab combined with fluorouracil plus cisplatin by analyzing biomarker measures within the tumor microenvironment and periphery (e.g., blood, serum, plasma) in comparison to clinical outcomes.
- To assess the subject's overall health status using the EQ-5D (EQ-5D-3L) index and visual analog scale.

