#### 7.5.4.2 PFS2/TSST

Hazard ratio (N+C vs CT; N+I vs CT) with its associated two-sided 95% CI will be estimated via a stratified Cox model with treatment arm as the only covariate in the model. PFS2/TSST for each treatment arm will be estimated and plotted using the KM product-limit method. Median PFS2/TSST time along with 95% CI will be constructed based on a log-log transformed CI for the survival function. 8,9

The PFS2/TSST rates and the source of PFS2/TSST event (death vs. PD vs. second next line systemic therapy) will be evaluated.

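### The SAP's PFS2/TSST rules can date the event later than its own earliest-event definition, and they count clinical progression that the protocol excludes

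*SAP*

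**What the plan says.** The PFS2/TSST text in SAP 4.3.1 has two layers. The definition lists progression after the next line of systemic therapy, "or start of the second next line systemic therapy or death from any cause, whichever occurs first". The rules that follow split subjects by whether they received any subsequent systemic therapy. For those who did, the first branch reads: "Subjects who had a disease progression after the start of the first subsequent anti-cancer systemic therapy, this disease progression date is the event date". The second branch opens with "Else if a subject died or start of the second next line systemic therapy" and takes the earlier of those two dates. The last branch censors at the last known alive date.

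The SAP definition counts "documented progression (radiographic or clinical progression) per investigator assessment". Protocol 8.3.3 defines the endpoint by objective progression, adds "Clinical deterioration will not be considered as progression", and leaves only the censoring details to the SAP. The SAP's own objective in Section 3.3 refers to "investigator-defined documented second objective disease progression or start of second subsequent therapy", and Protocol 1.3.3 says the same.

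SAP 7.5.4.2 plans a stratified hazard ratio with 95% CI, Kaplan-Meier curves and medians, and rates; in addition, "the source of PFS2/TSST event (death vs. PD vs. second next line systemic therapy) will be evaluated".

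**The concern.** There are two separate inconsistencies.

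The first lies within SAP 4.3.1. An earliest-event composite needs one minimum over all its components. The if/else structure instead gives progression priority over second-therapy start whatever their order. Nothing requires the progression to precede the second therapy, so a late progression can displace an earlier therapy start. Both the event time and the reported source of event are then wrong for that subject.

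The second is between SAP 4.3.1 and three other places: Protocol 1.3.3, Protocol 8.3.3 and SAP 3.3. Treatment is open-label and this progression is judged by the investigator, so whether clinical worsening counts is a matter of substance. It can decide whether a subject has an event at all.

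What is at stake is limited to a descriptive exploratory endpoint outside the alpha-controlled testing graph.

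**Working it through.** The plan gives no figure to reproduce here, so the check is logical.

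**Part 1: definition against derivation.** Take subjects with at least one subsequent systemic therapy. Let P be the first progression after that therapy started, T2 the start of the second subsequent systemic therapy, and D death. Each may be present or absent, and D comes last if present. Ties are ignored.

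- Definition: event date = min(P, T2, D) over the components that occurred.
- Derivation: P if P occurred; otherwise min(T2, D); otherwise censored.

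| Ordering | Definition | Derivation | Agree? |
|---|---|---|---|
| none | censored | censored | yes |
| P | P | P | yes |
| T2 | T2 | T2 | yes |
| D | D | D | yes |
| P, T2 | P | P | yes |
| T2, P | T2 | P | **no** |
| P, D | P | P | yes |
| T2, D | T2 | T2 | yes |
| P, T2, D | P | P | yes |
| T2, P, D | T2 | P | **no** |

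The two disagree in 2 of 10 orderings, exactly those in which T2 precedes P. In both, the date is late by P − T2 and the source is PD instead of therapy start. Event or censored status agrees in 10 of 10, so this defect moves event times and sources but not the event count.

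Illustration with assumed dates: T2 on day 300 and P on day 400. The derivation gives day 400 with source PD; the definition gives day 300 with source second therapy. The delay is 400 − 300 = 100 days, or 100 / 30.4375 = 3.3 months with the SAP's conversion factor.

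A subject is affected only if all of these hold: a first subsequent therapy, a second one, no progression recorded between them, and a progression recorded later.

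**Part 2: what counts as progression.**

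| Place | Progression counted |
|---|---|
| Protocol 1.3.3 (objective) | objective |
| Protocol 8.3.3 (endpoint) | objective; clinical deterioration excluded |
| SAP 3.3 (objective) | objective |
| SAP 4.3.1 (definition) | radiographic or clinical |

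Take a living subject with clinical progression only after next-line therapy and no second therapy. SAP 4.3.1 records an event; Protocol 8.3.3 does not. Unlike Part 1, this difference can change the event count.

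**Interaction.** If clinical progression counts, a switch prompted by documented clinical worsening already has P before T2, which limits the ordering error. If only objective progression counts, more subjects could have T2 first. The minimum rule is therefore needed under either choice.

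**The case against.** The governing definition is stated correctly, and the faulty bullets are labelled censoring rules, so a programmer who works from the definition gets the right date. That softens the first point but does not remove it: the bullets assign event dates and are the most specific instruction on the page.

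The affected group may be small or empty. Protocol 3.1.3 says "best response to the regimen and date of progression after second line therapy will be collected", and if progression is recorded by line of therapy, one that follows the start of a second subsequent therapy may never enter the derivation. The CRF is not visible, so this cannot be settled. It stands as a limit on consequence, as does the fact that 2 of 10 counts unweighted orderings and must not be read as 20% of subjects.

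The clinical-progression wording may be deliberate: the SAP version 4.0 history records that the definition was aligned with the sponsor's immuno-oncology core SAP. That explains its origin. It does not reconcile Protocol 1.3.3, Protocol 8.3.3 or SAP 3.3, all of which are current text.

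Two further wording differences would survive the main correction. The protocol and SAP 3.3 speak of a second progression, while SAP 4.3.1 takes any progression after the first subsequent therapy. SAP 4.3.1 also restricts the therapy component to systemic therapy, which the objectives do not. Both are fair points to settle in the same edit.

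**Conclusion.** Both inconsistencies hold on the current text. The derivation departs from the earliest-event definition whenever second subsequent therapy starts before the first recorded post-switch progression; it then dates the event late and misstates its source. The progression type in SAP 4.3.1 contradicts Protocol 8.3.3 and the objectives in both documents.

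Confidence is high that the conflicts exist. Their effect on results is unknown: the number of subjects affected, the change in hazard ratio or medians, and the net direction of the two effects cannot be obtained from the documents. With no alpha and no formal test on this endpoint, this is a correction worth making, not a threat to the trial's main conclusions.

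**What to change.** For subjects with at least one subsequent systemic therapy, replace the event branches in SAP 4.3.1 with one rule: event date = min(progression after start of first subsequent systemic therapy, start of second subsequent systemic therapy, death), with the source of event taken from whichever component is the minimum. If none occurred, censor at the last known alive date as now. This is one line of text and of derivation code and needs no new data.

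Then use one progression type in Protocol 1.3.3, Protocol 8.3.3, SAP 3.3 and SAP 4.3.1. Keeping clinical progression is a text amendment to the protocol and the SAP objective. Objective-only progression requires data that separate the two types. The follow-up items listed in Protocol 3.1.3, Protocol Table 5.1-5 and the SAP 2.1 follow-up text include a progression date but no progression type. Those lists are given as examples, so check the CRF before choosing. In the same edit, settle whether the progression must be a second one and whether the therapy component is limited to systemic therapy.
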